1.2 Specific Aims

Aim 1: Examine how TVS added to brief instructed mindfulness meditation can affect psychological state and performance. This aim is to show that TVS is particularly potent as a catalyst towards the types of experiences documented in experienced meditators.

Hypothesis 1.1: Positive affect and calmness: TVS added to mindfulness will increase subjective positive affect and calmness compared with mindfulness alone, particularly in individuals whose state is not strongly affected by mindfulness alone.

Hypothesis 1.2: Heightened states of awareness: TVS added to mindfulness will heighten state of awareness compared with mindfulness alone and particularly in individuals whose state is not strongly affected by mindfulness alone.

Hypothesis 1.3: Performance: TVS added to mindfulness will improve performance on visual attentional preference and empathy tasks and particularly in individuals whose state is not strongly affected by mindfulness alone and in individuals with increased positive affect and heightened state of awareness.

Aim 2: Examine how TVS added to brief instructed mindfulness meditation can affect physiological indicators of emotion regulation. Our overall hypothesis is that TVS, in combination with some other task, increases performance on that task by increasing emotion regulation. Mindfulness meditation is one such task that, without TVS may decrease emotion regulation in some people - TVS will counter that.

Hypothesis 2.1: TVS added to mindfulness increases physiological indicators of emotion regulation, including decreased galvanic skin response (GSR; index of sympathetic reactivity), increased heart rate variability (HRV; index of parasympathetic reactivity), and increased prefrontal gamma and theta band EEG compared with mindfulness alone during the intervention and follow-up tasks.

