2.5 Self-report Measures

--Pre-task

- 1) Demographic and screening questionnaire
- 2) Mindfulness attention awareness scale (Carlson & Brown, 2005)
- 3) Patient Health Questionnaire (Kroenke, Spitzer, & Williams, 2001)
- 4) Meditation experience questionnaire
- 5) Drug history questionnaire (Ventegodt & Merrick, 2003)
- 6) modified Differential Emotion Scale (Fredrickson, Tugade, Waugh, & Larkin, 2003)

--During tasks

- 1) Positive and Negative Affect Schedule (Watson, Clark, & Tellegen, 1988) will be given initially, and then after each intervention (meditation vs. meditation + TVS). This will also be given after the completion of each task (Mind in the Eyes, Global Local Task)

--Post-tasks

- 1) 5-Dimensional Altered State of Consciousness rating scale(Dittrich, 1998)

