Participants will undergo 2 blocks (randomized for order). 1) guided mindfulness meditation and 2) guided mindfulness meditation with TVS (0.1 Hz to 100 Hz) using SubPac, which is a marketed, wearable vibration technology that can deliver TVS, worn like a backpack. Participants will be wearing the SubPac (vest with vibration) the whole time but only during mindfulness with meditation, will the vest vibrate at various frequencies. The intensity of stimuli can vary from barely detectable through somewhat uncomfortable, but will not be painful. Similar vibratory stimuli have been standardly used in [name]'s lab. The intensity of the vibration will be adjusted to the subjects' comfort. Each of the interventions will be have a 12 minuted guided mindfulness meditation, with or without vibration coming out of the vest. They are given the choice to either sit in a desk chair or in a lounge chair, both in the same room. We advise them to concentrate to the meditation and the feelings in their body.

C) Cognitive and affective tasks:

These tasks are standard for our emotion/cognitive research lab.

1. Global-local visual processing task (Fredrickson & Branigan, 2005)

-- In general, images contain both local and global features. This task determines which attention is first directed, either at the local features (details, parts) or global features (the whole)

-- There will be a letter "T" made up of 4 smaller letter "T's". The smaller T's and the large "T" are incongruent in its orientation. The global feature of the letter "T" (the whole) will be of a particular orientation (up, down, left, right) and the local features (details, parts, in this case the 4 smaller letter "T's") will be of a different orientation (up, down, left, right). Participants will have to choose an answer by looking at the letter "T". There is no right answer, and the participant has the choose between 1) a letter "T" with congruent 4 smaller "T's" in the orientation of the global features (the whole) or 2) A letter "T" with congruent 4 smaller "T's" in the orientation of the local features (details, parts).

2. Reading the Mind in the Eyes test (Baron-Cohen, Wheelwright, Hill, Raste, & Plumb, 2001)

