### **Canonical Analysis Strategy**

Our canonical strategy for all aims in which outcome measures (e.g., physiology) are examined preintervention and post-intervention will as follows:

**Quality Control:** Data will be inspected visually and using our lab's standard algorithms to eliminate subjects, blocks, and trials in which data do not appear to be representative of the obtained measure, e.g., for EEG, data are eliminated when >3 channels have outlying means, standard deviations, are interpolated, or have unacceptably high levels of impedance.

**Preprocessing:** Data will be preprocessed using our lab's standard procedures which are consistent with industry standard procedures, e.g., via guidelines for psychophysiology from the Society for Psychophysiological Research. Outliers will be rescaled via windsorization.

**Data Reduction:** if more than one outcome measure of a given type (e.g., electrodes, for EEG) are employed, principal components analysis (PCA) will be used to yield aggregate indices across proposed outcome variables.

**Analysis:** Pre-intervention index values will be interacted with intervention type (mindfulness alone vs. TVS added to mindfulness) to explain variance in post-intervention index values using hierarchical regression; in the absence of an interaction, preintervention values will be regressed from post-intervention values before using intervention type as an independent variable to explain variance in post-intervention values in a residual regression analysis. The change in R^2 will be used as an effect size. Type I error will be controlled across the number of examined factors. Each type of outcome listed separately below will be interpreted as a statistically separate family for control of familywise error.

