### **Primary Outcome Measures**

### **1.Positive Affect Score from The Positive and Negative Affect Schedule**

The Positive Affect Score will be obtained after mindfulness meditation alone and after mindfulness meditation with TVS intervention. The Positive Affect Score will add the score on items 1, 3, 5, 9, 10, 12, 14, 16, 17, and 19. Scores can range from 10-50, with the highest score representing higher levels of positive affect

Analysis: Our canonical analysis will be used on positive affect scores

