### Other Pre-specified Outcome Measures: Moderation Analyses

#### **Canonical Moderation Analysis Strategy**

Moderation analyses will be analyzed by adding a third and fourth level to the hierarchical regressions described in our Canonical Analysis Strategy. On the third level, moderating variables are added. On the fourth level interactions of the moderating variables with primary and secondary outcome variables will be added. The change in R^2 from the third to the fourth level will be used as an effect size, and the significance of adding the interaction term on the fourth step will be interpreted as the significance of the moderation effect. Statistically significant moderation effects will be followed with creation of level curves for the 25th, 50th, and 75th percentiles for relevant variables to understand simple effects of the moderator on primary and secondary outcomes.

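### The pre-specified effect size, change in R-squared, has no sign, and no signed within-person difference or confidence interval is planned

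*SAP*

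**What the plan says.** **Effect size.** The SAP, Canonical Analysis Strategy, states: "The change in R 2 will be used as an effect size". All thirteen primary and secondary outcomes refer back to that strategy. The Canonical Moderation Analysis Strategy uses the same kind of index: "The change in R 2 from the third to the fourth level will be used as an effect size". Neither document names a mean difference, a signed coefficient, a standardised paired difference or a confidence interval as a reported result. The only planned signed display is a set of level curves, drawn only after a significant moderation effect.

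**Model.** A baseline-by-intervention interaction is tested first by hierarchical regression. If there is none, "preintervention values will be regressed from post-intervention values before using intervention type as an independent variable". No participant, period or sequence term is mentioned.

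**Design.** Protocol 2.6 makes this a within-person comparison: "Participants will undergo 2 blocks (randomized for order". For the affect scale, Protocol 2.5 says it "will be given initially, and then after each intervention (meditation vs. meditation + TVS".

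**Hypotheses.** Those governing the two primary outcomes have a direction. Hypothesis 1.1: "TVS added to mindfulness will increase subjective positive affect and calmness compared with mindfulness alone". Hypothesis 2.1: "TVS added to mindfulness increases physiological indicators of emotion regulation", with HRV, prefrontal gamma and prefrontal theta expected to rise and GSR to fall. SAP item 1 also fixes which way the affect scale runs: "Scores can range from 10-50, with the highest score representing higher levels of positive affect".

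**The concern.** A directional hypothesis needs an estimate that can come out on the wrong side. Change in R-squared cannot, because it is built from a squared effect. Adverse movement is a real possibility here: Hypothesis 2.2 expects mindfulness alone to worsen physiology in some people, so the plan itself allows for effects in both directions.

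The index also says nothing about size in units a reader can use, such as points on the 10 to 50 affect scale. Without an interval it says nothing about precision. Neither document states a sample size or power, so a small change in R-squared alone would not separate a small effect from too few participants.

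Finally, an effect measured within persons may be expressed as a share of variance that includes stable differences between persons. The reported size would then depend partly on how varied the recruits happen to be.

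**Working it through.** The plan gives no effect, SD, correlation, sample size or alpha, so there is no figure of its own to reproduce.

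**Inputs**
- From the documents: two conditions per person in random order; effect size is change in R-squared; baseline is regressed out if there is no interaction; no participant term is named.
- Assumed: SD of 1 in each condition; shift d = ±0.3; correlation ρ between a person's two conditions of 0.5, 0.7 or 0.8; one shared baseline with correlation r to each post value. The shared baseline is an assumption because the affect scale is also repeated after each task, and the baseline for the second block is not stated.
- Layout: two stacked rows per person.

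**Step 1: sign.** Condition contributes d²/4 to the variance of the stacked values, and total variance is 1 + d²/4. So:

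change in R² = (d²/4) / (1 + d²/4)

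For d = +0.3 and for d = −0.3 this is 0.0225 / 1.0225 = 0.022. As a check, 200,000 simulated persons with d = ±0.5 and ρ = r = 0.7 gave 0.0586 and 0.0589 (formula: 0.0625 / 1.0625 = 0.0588). The fitted coefficients were +0.497 and −0.499. The coefficient separates the two cases; the index does not.

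**Step 2: variance base.**
- Residual step: (d²/4) / ((1 − r²) + d²/4)
- Within-person share: d² / (d² + 2(1 − ρ))

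For d = 0.3 and r = ρ:
- ρ = 0.5: residual 0.0225 / 0.7725 = 0.029; within-person 0.09 / 1.09 = 0.083
- ρ = 0.7: residual 0.0225 / 0.5325 = 0.042; within-person 0.09 / 0.69 = 0.130
- ρ = 0.8: residual 0.0225 / 0.3825 = 0.059; within-person 0.09 / 0.49 = 0.184

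| ρ | Hierarchical | Residual (r = ρ) | Within-person | Within ÷ hierarchical | Within ÷ residual |
|---|---|---|---|---|---|
| 0.5 | 0.022 | 0.029 | 0.083 | 3.75 | 2.83 |
| 0.7 | 0.022 | 0.042 | 0.130 | 5.93 | 3.09 |
| 0.8 | 0.022 | 0.059 | 0.184 | 8.35 | 3.12 |

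Ratios use unrounded values.

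**Step 3: sensitivity.** Over a wider set of assumptions (d of 0.3 and 0.5; ρ from 0.3 to 0.9; r of 0, 0.5, 0.7 or √ρ), the within-person share is 1.4 to 14.1 times the residual-step value. With one shared baseline the two agree only if r² = (1 + ρ)/2, that is, if baseline explains all between-person variance.

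**The case against.** **The sign is not lost.** A reader might infer that the trial could not tell benefit from harm. The documents do not support that. The SAP calls change in R-squared an effect size, without excluding others; the planned regression contains intervention type and so yields a signed coefficient; and several outcome sections say what a higher or lower value means. This objection stands. What remains is that the signed coefficient and its interval are not pre-specified for reporting.

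**The dilution depends on the reading.** The residual step removes baseline variance, so the 4- to 8-fold figure does not apply there. The SAP is silent on a participant term rather than ruling one out, and if the plan does ignore pairing, that is also a fault of the model. Both parts stand and are reflected in the verdict.

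**The two shares are different quantities.** Share of total variance is not wrong in itself, and a paired standardised difference, d / √(2(1 − ρ)), also moves with ρ: for the same 0.3 SD shift it is 0.30, 0.39 or 0.47 at ρ = 0.5, 0.7 or 0.8. This is fair, and it is why outcome units should come first where they exist.

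**A single paired difference does not fit every outcome.** PCA scores have no natural units. Protocol 2.6 says the global-local task has no right answer, and SAP item 4 names no favourable direction. A retained interaction cannot be summarised by one difference. All three stand and shape the fix.

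**Conclusion.** The concern holds in a limited form. The pre-specified effect size is unsigned under any reading of the model, while the hypotheses for both primary outcomes are directional and no signed estimate or interval is planned. That part needs no assumption.

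The second part is conditional. If rows are stacked with no participant term, an assumed 0.3 SD shift with ρ of 0.5 to 0.8 gives a change in R-squared about 4 to 8 times smaller than the within-person share in the hierarchical step. In the residual step it is about 3 times smaller if r = ρ. None of these inputs is in the documents, and this part falls away if a participant term or paired differences put the share on within-person variance.

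A reader might go on to infer a fixed degree of understatement, or that every hypothesis is directional. The documents support neither: the correlations are not given, and Hypothesis 3.1, for example, speaks only of change.

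**What to change.** Amend the Canonical Analysis Strategy as follows.

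- For SAP items 1 to 12, make the main reported effect the within-person difference, TVS plus mindfulness minus mindfulness alone, with its 95% confidence interval, from a model with participant and period terms.
- Use outcome units where they exist and standardised units for PCA component scores, naming the standardising SD in advance.
- If the baseline-by-intervention interaction is retained, report the difference at the mean baseline and at stated baseline percentiles. The 25th, 50th and 75th would match the SAP's level curves.
- State the predicted direction for each outcome, including item 4.
- Call a directional hypothesis supported only if the interval, at the familywise-adjusted level, lies wholly on the predicted side of zero.
- Keep change in R-squared as a supplement.

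Item 13 is excluded: the 5D-ASC is answered once, for the experience judged more profound, so no within-person difference exists.

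The cost is SAP wording and a respecified model, which is more than an extra column of output. No new data are needed.

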### **Primary Outcome Measures**

### **1.Positive Affect Score from The Positive and Negative Affect Schedule**

The Positive Affect Score will be obtained after mindfulness meditation alone and after mindfulness meditation with TVS intervention. The Positive Affect Score will add the score on items 1, 3, 5, 9, 10, 12, 14, 16, 17, and 19. Scores can range from 10-50, with the highest score representing higher levels of positive affect

Analysis: Our canonical analysis will be used on positive affect scores

### 2.Heart Rate Variability (HRV) during mindfulness meditation

HRV, an index of parasympathetic reactivity, will be obtained during mindfulness meditation alone and during mindfulness meditation with TVS intervention. Increased HRV indicates increased parasympathetic reactivity, which suggests an increased physiological indicator of emotion regulation.

Analysis: Our canonical analysis strategy will be employed on HRV measured during the intervention

### **Secondary Outcome Measures**

### 3. Negative Affect Score from The Positive and Negative Affect Schedule

The Negative Affect Score will be obtained after mindfulness meditation alone and after mindfulness meditation with TVS intervention. The Negative Affect Score will add the score on items 2,4,6,7,8,11,13,15,18, and 20. Scores can range from 10-50, with lower score representing lower levels of negative affect.

Analysis: Our canonical analysis will be used on negative affect score

# 4. Global local visual processing task - percent local identifications

There will be 40 images for each task. This task determines which attention is first directed, either at the local features (details, parts) or global features (the whole). Out of 40, we can determine how many local features were picked and how many global features were picked. The task will be done twice and the amount of global features vs. local features chosen will be compared with one another.

Our canonical analysis will be used on performance measures on the global local visual processing tasks

#### 5. Mind in the Eyes Test - percent correct identifications

Participants will see a picture of a person only with the eyes present. There will be four words that describes the possible mood of the participant. The participant will be asked to choose the adjective that fits best with eye mood conveyed by picture of the person when only the eyes can be observed. This task will be done twice, and the amount of correct answers will be compared with one another

Our canonical analysis will be used on performance measures on the mind in the eyes test

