2.6 Tasks

OUTLINE of procedures during the tasks

--Calibration (EEG, Pupil/Eye tracking, baseline GSR/EKG, vibration)

--Intervention 1: Meditation*

--Tasks 1: Global-Local Test, Mind in the Eyes

--Intervention 2: Meditation and TVS*

--Tasks 2: Global-Local Test, Mind in the Eyes

*Participant will be randomized whether they get meditation first or meditation and TVS first

All of tasks will be video recorded (calibration, intervention, tasks). The videos may be reviewed by study personnel and investigators for quality assurance, training purposes, or analysis. Physical backups are kept in locked filing cabinets and are labeled with subject identification number and date only. Electronic video or audio files will be stored on a password protected server which only study personnel

can access. Video and audio recordings will be kept indefinitely and may later be reviewed by other researchers. Participants may request destruction of video or audio recordings, or may also request not to be audio or video taped.

Physiological measurements during tasks include galvanic skin response (GSR) measured using electrodes placed on the index and middle finger, pupillary dilation indices, EKG (electrocardiography) which will be measured using three electrodes (left clavicle, right clavicle, and under the right rib), respiration (using a respiration belt), and EEG (mobile EEG monitor on head) will be collected during: 1) calibrations, 2) interventions and 3) cognitive and affective tasks. All of the stated physiological measurements will be collected except pupillary dilation indices will not be collected during interventions (meditation, meditation + TVS) because participants are encouraged to relax and are given the opportunity to close their eyes during those times.

A) Calibrations:

Calibration tasks will initially be completed for physiology collection including a vibration calibration that allows assessment of individualized vibration frequency preferences, a GSR/EKG calibration at baseline, EEG calibration at baseline and pupillary dilation calibration. During the EEG calibration, there are some images that may evoke negative emotions, which is in the introduction, and participants are encouraged to stop the calibration at any time if they feel uncomfortable with the images.

B) Interventions:

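### The SAP assigns Global-Local and Mind in the Eyes a pre/post model that cannot be fitted, because neither task is given before an intervention and no substitute baseline is named

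*SAP*

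**What the plan says.** Protocol section 2.6 outlines the session in order. It opens with "Calibration (EEG, Pupil/Eye tracking, baseline GSR/EKG, vibration", which contains neither task. Intervention 1 follows, then "Tasks 1: Global-Local Test, Mind in the Eyes", then Intervention 2, then "Tasks 2: Global-Local Test, Mind in the Eyes". Order is randomised: "Participant will be randomized whether they get meditation first or meditation and TVS first".

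The SAP's Canonical Analysis Strategy is introduced for outcomes observed both before and after the intervention. Its first step is "Pre-intervention index values will be interacted with intervention type". If there is no interaction, the second step regresses the pre-intervention value out of the post-intervention value and then tests intervention type.

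SAP outcome 4 describes the data as "The task will be done twice and the amount of global features vs. local features chosen will be compared with one another" and then says "Our canonical analysis will be used on performance measures on the global local visual processing tasks". SAP outcome 5 has the same structure: "This task will be done twice, and the amount of correct answers will be compared with one another", followed by a sentence assigning the canonical analysis. Neither section says what the pre-intervention value is.

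**The concern.** Every administration of these two tasks follows an intervention, yet the named model needs a score that precedes one. Each outcome section therefore describes two analyses: a direct comparison of two scores, which the schedule supports, and the canonical regression, which it does not. The choice is left to the analyst.

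Hypothesis 1.3 (performance) rests on these two outcomes and Hypothesis 3.2 also uses them. Moderation analyses 14 to 16 add levels to the same regression, so they inherit the problem.

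The nearest available stand-in is the Tasks 1 score as the pre value for Tasks 2. That would discard block 1 as an outcome, turn a within-person design into a between-sequence comparison, and adjust for a score already affected by whichever condition came first.

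**Working it through.** **Step 1: is there a pre-intervention score?**

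- Calibration (Protocol 2.6): EEG, pupil, GSR/EKG and vibration; neither task.
- Number of administrations (SAP outcomes 4 and 5): two of each task, matching Tasks 1 and Tasks 2, both after an intervention.
- Contrast: Protocol 2.5 gives the PANAS once at the start as well as after each intervention, so it has a baseline.
- Contrast: for the 5D-ASC, SAP outcome 13 names a different variable, prior altered state of awareness, for the pre-intervention term.

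Outcomes 4 and 5 have neither a baseline nor a named substitute. Both steps of the canonical model lack an input.

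**Step 2: what would happen if Tasks 1 were used as the pre value for Tasks 2?**

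The documents give no sample size, effect size, SD, retest correlation or washout, so there is no figure of the plan's to reproduce. Assumptions: SD 1 for each score; 1:1 sequences; TVS effect τ = 0.30 SD; correlation ρ between the two scores within sequence; carryover λ from TVS in block 1 into Tasks 2; common period shift π.

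| Sequence | Mean, Tasks 1 | Mean, Tasks 2 |
|---|---|---|
| TVS first | τ | π + λ |
| TVS second | 0 | π + τ |

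The difference, TVS second minus TVS first, is −τ on Tasks 1 and τ − λ on Tasks 2.

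- Covariate adjustment: (τ − λ) − ρ(−τ) = τ(1+ρ) − λ.
- The SAP's residual regression: (τ − λ) + bτ, where b = [ρ − τ(τ − λ)/4] / [1 + τ²/4]. For ρ = 0.5 and λ = 0, b = (0.5 − 0.0225)/1.0225 = 0.467, giving 0.30 + 0.467 × 0.30 = 0.44.

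Estimates when the truth is 0.30:

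| ρ | Covariate, λ = 0 | Residual, λ = 0 | Covariate, λ = 0.15 | Covariate, λ = 0.30 |
|---|---|---|---|---|
| 0.3 | 0.39 (+30%) | 0.38 | 0.24 | 0.09 |
| 0.5 | 0.45 (+50%) | 0.44 | 0.30 | 0.15 |
| 0.7 | 0.51 (+70%) | 0.50 | 0.36 | 0.21 |

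Simulation with 400,000 participants per scenario agreed with these to within 0.01. For a positive effect, the covariate-adjusted estimate is too large only when ρτ exceeds λ.

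Two limiting cases:

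- With τ = 0 and λ = 0 the estimate is 0. In simulation at ρ = 0.6, covariate-adjusted type I error was 0.050 to 0.053 for 20 to 60 participants.
- A negative effect is magnified in the same way: τ = −0.30 becomes −0.30 × 1.5 = −0.45 at ρ = 0.5 without carryover.

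**Step 3: the direct within-person comparison.**

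Half the between-sequence difference in (Tasks 2 − Tasks 1) is ½[(π + τ) − (π + λ − τ)] = τ − λ/2. The period shift cancels. For τ = 0.30 this gives 0.30, 0.225 and 0.15 at λ = 0, 0.15 and 0.30, whatever ρ is.

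Without period adjustment, and with a share p of participants receiving TVS second and no carryover, the mean paired difference is τ + π(2p − 1). The allocation ratio is not stated, so a period term is needed.

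**The case against.** A reader might infer that the plan as written inflates the TVS effect. The documents do not support that. The SAP never says that Tasks 1 will serve as the pre value, and its handling of the 5D-ASC shows that it sometimes places another variable in that term. Even under the substitution, the direction is not fixed. Protocol 2.2 places everything on one assessment day and no washout is described, so carryover cannot be excluded, and enough of it makes the estimate too small. A true null without carryover produces no false effect, and a harmful effect is magnified as readily as a beneficial one. Nor is the Tasks 1 score always a post-TVS score: it follows TVS in one sequence and mindfulness alone in the other. All of this stands, and it limits the claim about bias.

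It can also be said that the SAP already describes the right comparison, and that the canonical strategy is introduced only for outcomes with pre and post values. Both statements are true, but the canonical analysis is still named expressly for both tasks, so the contradiction remains.

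Finally, these are secondary outcomes. Positive affect has an initial PANAS and calibration includes a baseline GSR/EKG recording, so the two primary outcomes do not share this gap. That lowers the priority without removing the point.

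**Conclusion.** The analysis named for SAP outcomes 4 and 5 cannot be run as written, and it conflicts with the direct comparison described in the same sections. This follows from the documents alone and is firm.

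The size of any bias is conditional. It arises only if Tasks 1 is substituted as the pre value, and then depends on an effect size, correlation and carryover that the documents do not give. With no carryover and ρ of 0.3 to 0.7, the covariate-adjusted estimate is 30% to 70% too large in magnitude, and slightly less with the SAP's residual regression. With carryover above ρτ it is too small. The uncertain direction is itself a reason to rule out the substitution in advance. The within-person contrast is unbiased without carryover, but it is not immune to it.

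This should be fixed before analysis. It concerns two secondary outcomes that support Hypotheses 1.3 and 3.2, and it does not undermine the primary analyses.

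**What to change.** In SAP outcomes 4 and 5:

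- Replace the sentence assigning the canonical analysis with a within-person crossover comparison of the score after TVS and the score after mindfulness alone. Include a period (order) term and no pre-intervention term.
- State that the Tasks 1 score will not be used as the pre-intervention value for Tasks 2.
- State that, for these two outcomes, moderation analyses 14 to 16 add the moderator and the moderator-by-condition interaction to this crossover model.
- Acknowledge that the comparison assumes no carryover, and that carryover λ would move the estimate to τ − λ/2.

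The cost is a few SAP sentences, with no extra task administration, participants or session time. The interaction of pre value with intervention type is lost for these two outcomes, but the schedule could not supply it.
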